APPENDIX A:

Planned Tables and Figures

Version: 1.0

	Title Statistical Analysis Plan 43CH1507	Doc id MA-32268
--	---	----------------------------------

Effective date: 2017-04-21 09:20

Effective

Version: 1.0

1 Study Information

1.1 Background

1.1.1 Study design

This is a randomized, evaluator-blinded, no-treatment controlled study in subjects with Midface Volume Deficit and/or Midface Contour Deficiency. The first 2 eligible subjects for each Treating Investigator will receive treatment as Group A. Before start of enrolment into Group B, the injection technique will be evaluated by the Sponsor. This evaluation will be performed after the first treatment of the subjects in Group A for each Treating Investigator. Subjects in group B will be randomized either to the Treatment group or the Control group in a 3:1 ratio.

Summaries of the results for Group A and B will be done separately in the study report.

Each subject assigned to Group A or to the Treatment group in Group B will receive an initial treatment on Day 1. A touch-up treatment may be performed 4 weeks after the initial treatment if optimal midface augmentation has not been obtained.

Subjects assigned to the Control group in Group B will not receive treatment at baseline but will be offered a treatment at Month 6, and an optional touch-up treatment 4 weeks later.

1.1.2 Number of subjects and randomization

Approximately 148 subjects will be randomized in a 3:1 ratio to treatment with Restylane Perlane Lidocaine (Perlane-Lido) or to no treatment. The randomization will be stratified by site.

1.2 Study Objectives

1.2.1 Primary Objective

The primary objective is to demonstrate superiority of Perlane-Lido relative to no-treatment in the treatment of Midface volume Deficit and/or Midface Contour Deficiency by comparing the percent responders, defined by at least 1 point improvement from baseline on the MMVS on both sides of the face, as measured by blinded evaluator at 6 months.

CCI

 GALDERMA	<small>Title</small> Statistical Analysis Plan 43CH1507	<small>Doc id</small> MA-32268
---	---	--

CCI

1.2.3 Safety objectives and endpoints

The safety objectives and endpoints are:

- To evaluate the safety of Perlane-Lido during the whole study by collecting Adverse Events (AEs).

CCI

1.3 Efficacy assessment

For all assessments, baseline will be defined as the observation that is closest to but prior to study treatment on Day 1. Likewise, change from baseline will be calculated as the value at a given time point minus the baseline value.

1.3.1 Medicis Midface Volume Scale (MMVS)

MMVS is a 4-grade scale assesses the fullness of the midface from Fairly Full (1) to Substantial Loss of Fullness (4) as described below.

2017-04-21 09:20

Effective date:

Effective

Version: 1.0

The blinded evaluator will rate the subject's right and left midface for severity of volume deficiency using the MMVS at screening, baseline, ^{CCI} 6, ^{CCI} months after last treatment in Group A and Treatment group; and at screening, baseline, ^{CCI} 6 months after randomization, ^{CCI} in the Control group.

[figure not shown]
CCI

Table 1-1. The Medicis Midface Volume Scale.

MMVS	
1	Fairly full midface
2	Mild loss of fullness in midface area
3	Moderate loss of fullness with slight hollowing below malar prominence
4	Substantial loss of fullness in the midface area, clearly apparent hollowing below malar prominence

CCI

 GALDERMA	<small>Title</small> Statistical Analysis Plan 43CH1507	<small>Doc id</small> MA-32268
---	---	--

[figure not shown]

1.4 Efficacy endpoints

1.4.1 Primary efficacy endpoint

Responder rate based on the MMVS as assessed by the blinded evaluator at 6 months after last treatment for the Treatment group, and at 6 months after randomization for the Control group.

A responder is defined as a subject who achieves a score of at least 1 grade improvement from baseline to 6 months on both sides of the face.

Effective date: 2017-04-21 09:20

Effective

Version: 1.0

 GALDERMA	<small>Title</small> Statistical Analysis Plan 43CH1507	<small>Doc id</small> MA-32268
CCI		

1.5 Safety assessments

The methods for collecting safety data are described in Section 8 of the Clinical Study Protocol

 GALDERMA	Title Statistical Analysis Plan 43CH1507	Doc id MA-32268
--	---	----------------------------------

Effective date: 2017-04-21 09:20

(CSP) and include assessments of **CCI**
 [REDACTED] Adverse Events (AE), Serious Adverse Events (SAE), and Device Deficiency.

A two-point scale (“Yes” or “No” response) will be used for the causality assessments. The Treating Investigator should be asked to indicate a response to each of the following questions in the eCRF:

- “Do you consider that there is a reasonable possibility that the event may have been caused by the study product?”
- “Do you consider that there is a reasonable possibility that the event may have been caused by the injection procedure?”

If any of these questions is answered with a ‘Yes’, the AE will be considered related. These assessments will also be reviewed by the Sponsor. In the case of a disagreement, the AE will be classified as ‘Related’.

Time to onset of an AE will be derived as the start date minus Day 1. If the start date is missing, it will be assumed that the AE started on Day 1.

Duration of an AE will be derived as the stop date minus the start date + 1. If the start date is missing, it will be assumed that the AE started on Day 1. Missing stop date will not be imputed and therefore no duration will be calculated in these cases. Instead, the number of AEs that were ongoing at the end of the study will be given.

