3.4.2 Adverse events

All AEs will be coded according to MedDRA. All AE summaries defined below will be presented by treatment (no treatment at baseline vs. all treated subjects (at baseline and Month 6)).

The number of subjects with AEs related to study product or injection procedure as well as the number of events will be summarized by SOC and preferred term (PT). In addition, AEs related to study product or injection procedure will be summarized by SOC, PT and intensity. The number of days to onset and the duration of related AEs will be summarized by SOC and PT using mean, SD, min, max and median.

Serious AEs and device deficiencies will be listed, if applicable.

Non related AEs will be summarized by SOC, PT, and intensity.

CCI

[figure not shown]

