Injection site xxx														
Injection site xxx														
ALL														

Note: Treatment with Perlane-Lido columns include data from subjects in the Perlane-Lido group after their initial treatment at baseline, as well as data from subjects in the Control group after their initial treatment at Month 6.

% = 100*n/N

 GALDERMA	Title Statistical Analysis Plan 43CH1507	Doc id MA-32268
---	---	----------------------------------

Table A 38. Action taken due to related TEAEs by MedDRA System Organ Class and Preferred Term (Safety)

[figure not shown]
System Organ Class Preferred Term	Action Taken							
	No treatment at baseline N=xx				Treatment with Perlane-Lido N=xx			
	None	Medication treatment	Non-pharmacological treatment or other procedures/tests	Subject withdrawn	None	Medication treatment	Non-pharmacological treatment or other procedures/tests	Subject withdrawn
General disorders and administration site conditions								
Injection site xxx								
Injection site xxx								
SOC 2								
PT 1								
PT 2								
...								
All								

Table A 39. Unrelated TEAEs by MedDRA System Organ Class, Preferred Term and intensity (Safety)

As Table A 35

[figure not shown]
 GALDERMA	<small>Title</small> Statistical Analysis Plan 43CHI1507	<small>Doc id</small> MA-32268
---	---	--

CCI

 GALDERMA	<small>Title</small> Statistical Analysis Plan 43CH1507	<small>Doc id</small> MA-32268
---	--	--

CCI

 GALDERMA	<small>Title</small> Statistical Analysis Plan 43CH1507	<small>Doc id</small> MA-32268
---	--	-----------------------------------

CCI

[figure not shown]

Figure A 11. Proportion of subjects affected by a specific event (to any intensity level) after touch-up (Safety)

As Figure A 10

 GALDERMA	Title Statistical Analysis Plan 43CH1507	Doc id MA-32268
--	---	----------------------------------

2017-04-21 09:20

Effective date:

Effective

Version: 1.0

SIGNATURES PAGE

Date	Signed by
2017-04-20 15:12	PPD
Justification	Approved by Owner
2017-04-21 06:29	PPD
Justification	Approved by Technical Expert
2017-04-21 07:58	PPD
Justification	Approved by Project Manager
2017-04-21 08:38	PPD
Justification	Approved by Technical Expert
2017-04-21 09:20	PPD
Justification	Approved by Technical Expert

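### AE time to onset is counted from Day 1 for all subjects, although controls' events after their Month 6 injection are pooled into the Perlane-Lido column, so a same-day reaction there would be reported at about 183 days

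*SAP*

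**What the plan says.** SAP 1.5 gives the onset rule without distinguishing the arms: "Time to onset of an AE will be derived as the start date minus Day 1". The rule for incomplete dates uses the same anchor: "If the start date is missing, it will be assumed that the AE started on Day 1".

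The arms are first injected at different times. SAP 1.1.1 has Group A and the Treatment group injected on Day 1, whereas "Subjects assigned to the Control group in Group B will not receive treatment at baseline but will be offered a treatment at Month 6". Either arm may also have a touch-up four weeks after its first session.

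SAP 3.4.2 splits all AE summaries into untreated experience and all treated subjects, and the treated cohort includes controls from Month 6. The note under Table A 37, the onset table itself, says that the Perlane-Lido column holds Treatment group data "as well as data from subjects in the Control group after their initial treatment at Month 6". The planned content is: "The number of days to onset and the duration of related AEs will be summarized by SOC and PT using mean, SD, min, max", plus the median.

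**The concern.** The rule works where Day 1 is an injection day. It fails for controls, whose treated experience begins about six months after Day 1. In Table A 37 their immediate reactions would look like reactions arising half a year after exposure.

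The trial's own documents treat latency as informative. Protocol 2.4.2 reports a related serious event of late-onset inflammation in the earlier US midface study. The IFU in Protocol Appendix 3 distinguishes inflammation that starts soon after injection from inflammation delayed by up to several weeks. Within Table A 37, a reader could not tell a control's immediate reaction from a true late event.

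A secondary point concerns missing start dates. A control's event after the Month 6 injection with no start date would be set to Day 1, before any exposure. That contradicts the column definition and could drop the event from the treated column. If a stop date is present, it would also add about 183 days to the duration in Table A 36.

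**Working it through.** The readable text states no onset figure to reproduce. The one related design figure agrees: 148 × 3/4 = 111 and 148 × 1/4 = 37 (Protocol Synopsis).

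**Which day is Day 1 for a control?**
- Protocol Table 2 and Protocol 4.8.2.2 label the controls' untreated baseline visit D1.
- SAP 1.3 ties baseline to Day 1: "baseline will be defined as the observation that is closest to but prior to study treatment on Day 1". If Day 1 were a control's Month 6 injection day, the control baseline would move to Month 6. The primary endpoint in SAP 1.4.1 (change from baseline to 6 months after randomisation) would then lose its meaning for controls.
- SAP 1.4.1 names a different origin for each arm where one is intended. SAP 1.5 does not.
- The readable part of SAP 5 changes the AE cohorts but leaves the onset origin alone.

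So Day 1 for a control is the randomisation visit.

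**Offset for one event.** Controls are treated at 6 months ± 1 week after randomisation (Protocol Table 2). Six calendar months is 181 to 184 days, about 183. With the window, the range is 181 − 7 = 174 to 184 + 7 = 191 days. A same-day reaction should have onset 0 but is reported at 174 to 191 days.

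**Effect on the pooled mean.** Assumptions: 111 Treatment and 37 Control subjects; reactions on the day of injection, the typical pattern in Protocol 8.4.8; equal related events per treated subject; offset 183 days. Let u be the share of controls who accept treatment, which is unknown. The control share of the column is p = 37u / (111 + 37u). Against a first-injection origin, the mean is too long by 183p at any touch-up rate.

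| u | p | Mean shift (days) |
|---|---|---|
| 0.25 | 9.25/120.25 = 0.077 | 14.1 |
| 0.50 | 18.5/129.5 = 0.143 | 26.1 |
| 0.75 | 27.75/138.75 = 0.200 | 36.6 |
| 1.00 | 37/148 = 0.250 | 45.8 |

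If controls have r times the Treatment group's event rate, p = 37ur / (111 + 37ur). For r = 0.5 to 1.5, the shift is 14.1 to 36.6 days at u = 0.5 and 26.1 to 61.0 days at u = 1.

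**Touch-ups.** Let t be the share of treated subjects with a touch-up at 28 days, with one same-day reaction per session. Against a most-recent-injection origin the correct onset is always 0, and the shift is 183p + 28t/(1 + t). At t = 0.5 the second term is 9.3, which gives 23.4, 35.5, 45.9 and 55.1 days for the four values of u.

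**SD at u = 1.** With t = 0, the SD goes from 0 to 183 × √(0.25 × 0.75) = 79.2 days. With t = 0.5 and a first-injection origin, it goes from 28 × √(1/3 × 2/3) = 13.2 to √(79.2² + 13.2²) = 80.3 days.

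**Median.** As written, the share of events at onset 0 is (1 − p)/(1 + t). The median leaves 0 for 28 days once this falls below one half, that is when t > 1 − 2p: 0.85, 0.71, 0.60 and 0.50 for u = 0.25, 0.50, 0.75 and 1.00. With few touch-ups it stays at 0.

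**Maximum.** Any related AE in a control treated within the window puts the maximum at about 174 days or more.

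**The case against.** The strongest reply is that SAP 1.5 leaves Day 1 undefined, and elsewhere in the readable SAP the term appears alongside study treatment. A programmer could read it as the day of first injection. Assigning events to the column already requires each control's injection date, and a same-day reaction at 183 days would be conspicuous at output review. Parts of SAP 1.6, 3.1, 3.4.2 and 5 are redacted, so an exception may sit there. The damage is also confined: safety data are listed by subject, serious AEs are listed individually, Group A is summarised separately, and Figures A 10 and A 11 are titled by treatment session. Missing start dates may be rare, since the start date is a recorded AE item and eCRFs are reviewed in full.

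Some of this stands. SAP 1.3 is loosely worded for controls, a redacted exception cannot be excluded, and the listings would let a reader recover the true latency. The frequency of missing start dates is unknown, so that point remains secondary. The alternative reading of Day 1 does not stand. It conflicts with the protocol's visit labels and with the control baseline needed for the primary endpoint. Hoping that a programmer will depart from the written rule, or that a reviewer will notice the result, does not replace a correct rule.

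**Conclusion.** The concern holds. Followed as written, the onset rule gives a wrong result for controls treated at Month 6: about 183 days for a reaction that began on the day of injection. Under the stated assumptions, the pooled mean is too long by about 14 to 46 days as uptake runs from 25% to 100%, against a first-injection origin. At full uptake with no touch-ups, the SD rises from 0 to about 79 days. The maximum is distorted once any treated control has a related event; the median is affected only if touch-up reactions are common.

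These sizes rest on unknown uptake, touch-up and event rates, and on the absence of an exception in redacted text. The six-month offset for a single event depends only on that last condition. For dated events, AE counts, relatedness, intensity and duration are unaffected, as are all efficacy analyses. This should be fixed, but it bears on descriptive safety reporting and not on the trial's inference.

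**What to change.** - In SAP 1.5 and the Table A 37 footnote, derive onset in the Perlane-Lido column from the subject's own injection date: Day 1 for the Treatment group, the actual Month 6 treatment date for controls. Keep Day 1 as the origin in the untreated column.
- State whether the origin is the first or the most recent injection, and apply it alike to both arms. Either removes the six-month offset. A first-injection origin still places same-day touch-up reactions at about 28 days. A most-recent-injection origin avoids that, but counts a delayed reaction to the first session from the touch-up if it appears afterwards.
- For a control's event first reported after the Month 6 treatment, impute a missing start date no earlier than that treatment date, and report how many dates were imputed.

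The cost is a few lines of SAP wording, one footnote and modest derivation code. Protocol 6.6.5 already has the date of each injection recorded in the eCRF, so no new data are needed.

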1.6 Safety endpoints

Safety endpoints include:

(vii) *Incidence of AEs*

All AEs collected at all visits following screening.

CCI
 [REDACTED]

Version: 1.0

 GALDERMA	Title Statistical Analysis Plan 43CH1507	Doc id MA-32268
--	---	----------------------------------

2 Analysis Populations

The following populations will be defined:

- Safety Includes all subjects in Group B who were treated with Perlane-Lido or randomized to no-treatment group. Subjects are analyzed based on the as treated principle.
- Full Analysis Set (FAS) Includes all subjects in Group B who were treated with Perlane-Lido or randomized to no-treatment group. Subjects are analyzed according to the randomisation assignment.
- Per Protocol (PP) Includes all subjects in FAS that comply to the protocol procedures with no deviations that can affect the evaluation of the primary variable.

The FAS population is the primary population for all efficacy analyses. All safety analyses will be based on the Safety population.

3 Statistical Methods

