2.4.2 Clinical Documentation

Except for nasolabial folds treatment^{4,5} Perlane-Lido also has been proven safe and efficacious for cheek augmentation and correction of age-related midface contour deficiencies in a clinical trial⁶ (MA-1400-05) performed in US. Perlane-Lido is approved under the brand name Restylane® Lyft with Lidocaine in US.

The study was an evaluator-blinded, no treatment controlled study of 200 subjects who were randomized in a 3:1 ratio to receive Perlane-Lido in the midface or no treatment at baseline. The primary effectiveness objective was to identify if Perlane-Lido was more effective in midface augmentation than no treatment as determined by the blinded evaluator's assessment of midface fullness using the Medicis Midface Volume Scale (MMVS) at Month 2 following baseline/Day 0.

In the Perlane-Lido group, 88.7% (133/150 subjects) were MMVS responders in the right and left midface combined. In the no treatment group at Month 2, the proportion of MMVS responders from baseline was 16.0% (8/50 subjects). The difference in the proportion of

 GALDERMA	Title 43CH1507 Perlane Lido midface study protocol	Doc id MA-30843
--	---	----------------------------------

Effective date: 2016-09-07 11:57

Effective

Version: 4.0

MMVS responders from baseline for right and left midface combined, between the Perlane-Lido and no treatment groups, was statistically significant ($p<0.001$) in favor of Perlane-Lido treatment; therefore, the primary effectiveness assessment was met.

The proportion of MMVS responders was also statistically significant at all other evaluation time points through Month 12 for both the blinded evaluator **CCI** [REDACTED], as outlined in the secondary objectives.

The study also indicates that the safety profile of Perlane-Lido is maintained. The majority of events were mild, considered tolerable and resolved in 2 – 7 days. Bruising tended to have a longer duration with the majority of subjects resolving between 8 and 14 days. Two subjects (1%, 2/199) reported four serious adverse events (SAEs) that were considered to be related to the device and/or the procedure. One subject reported implant site inflammation (late onset inflammatory reactions) in both cheeks at separate times. The second subject experienced implant site hematomas in the right cheek and implant site infection/abscess. Treatment of the SAEs included NSAIDs, antibiotics, incision and drainage and, hyaluronidase. All events resolved.

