4.4 Randomization and blinding

4.4.1 Randomization

Approximately 148 subjects will be randomized in a 3:1 ratio to treatment with Perlane-Lido or to no treatment. Before starting the study, a computer generated randomization list will be prepared under the supervision of a designated statistician.

Each subject will be assigned a subject number as they arrive for the treatment visit. For group B, randomization will be assigned via the eCRF system. At the time for randomization, the subject's initials, date of randomization, subject number, randomized treatment, and the signature of the Investigator must be documented in a randomization log. The treatment information will be kept by the Treating Investigator during the study not to be disclosed to the Blinded Evaluator.

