4.4.2 Blinding

Only the evaluator will be blinded, both treating investigator and subjects will be open-labelled.

The Blinded Evaluator shall not be allowed to retrieve study supplies or to be present during opening of the study supplies or injections. The Treating Investigator is not allowed to discuss treatments with the blinded evaluator or the subjects. All documents with information on study products shall be kept in a separate binder not available to the blinded evaluator.

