3.3.2 Handling of missing data

Number of missing values will be summarized and reported as appropriate. The baseline observation carried forward (BOCF) method will be used as the primary imputation method to handle missing data on MMVS up to the Month 6 visit in the FAS analysis set. This strategy is a conservative approach as it treats subjects with missing data as non-responders. Impact of missing data on the primary analysis for Month 6 endpoint will be evaluated by performing sensitivity

	Title Statistical Analysis Plan 43CH1507	Doc id MA-32268
--	---	----------------------------------

Effective date: 2017-04-21 09:20

Effective

Version: 1.0

analysis based on the PP population. In addition, missing data for the primary analysis will also be handled using the multiple imputation (MI) method.

All other endpoints will be analyzed on available data, i.e. no imputations will be done.

If the baseline value is missing, the screening value will be used instead.

Use of MI

The imputation using MI will assume a Missing Completely at Random (MAR) mechanism. The MI procedure of the SAS® system will be used to generate five sets of data with missing values imputed from observed data. It is expected that the pattern of missing data will be monotonic, with slight deviations being corrected by the Markov Chain Monte Carlo (MCMC) method of the MI procedure. Linear regression will be employed to model the missing MMVS score, with the following covariates included in the imputation model: treatment and non-missing data from earlier time points (baseline CCI [REDACTED]). The imputed datasets will be analyzed using the methodology described for the primary analysis of responder rates at Month 6. The results from the analysis of the multiple imputed datasets will be presented as appropriate. The seed number to be used will be 431507 (the clinical trial number of this study, with the letters removed).

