 GALDERMA	Title Statistical Analysis Plan 43CH1507	Doc id MA-32268
---	---	--------------------

Table A 16. MMVS responder rate by treatment and side of the face at Month 6, Blinded Evaluator (FAS)

Assessment/Time Point	Treatment Group	# of Subjects in FAS	# of Responders	Proportion of Responders	95% Confidence Interval	P-Value
Right and Left Midface Combined at Month 6	Perlane-Lido	Xx	Xx	X.XX	X.XX, X.XX	
	Control	Xx	Xx	X.XX	X.XX, X.XX	
	Difference	-	-	X.XX	X.XX, X.XX	X.XX
Right Midface at Month 6	Perlane-Lido	Xx	Xx	X.XX	X.XX, X.XX	
	Control	Xx	Xx	X.XX	X.XX, X.XX	
	Difference	-	-	X.XX	X.XX, X.XX	X.XX
Left Midface at Month 6	Perlane-Lido	Xx	Xx	X.XX	X.XX, X.XX	
	Control	Xx	Xx	X.XX	X.XX, X.XX	
	Difference	-	-	X.XX	X.XX, X.XX	X.XX

Note: Subjects with a missing MMVS have their values imputed using BOCF up to Month 6.

Note: Responder is defined as a subject with an improvement of at least one grade on the MMVS from baseline.

Note: Responder rate is calculated as the number of Responders at the visit of interest divided by the number of subjects in the FAS population for the specific treatment group.

Note: P-values for the difference in proportions are based on the Fisher's Exact test.

Note: 95% Confidence Intervals are two-sided confidence intervals calculated using the exact interval.

Table A 17. MMVS responder rate by treatment and side of the face at Month 6, Blinded Evaluator (PP)

As Table A 16 (only Left and Right Side Combined)

Note: No imputation is used for PP analysis. Only subjects with complete data are included.

Note: Responder is defined as a subject with an improvement of at least one grade on the MMVS from baseline.

Note: Responder rate is calculated as the number of Responders at the visit of interest divided by the number of subjects in the PP population for the specific treatment group.

CCI

 GALDERMA	Title Statistical Analysis Plan 43CH1507	Doc id MA-32268
--	---	----------------------------------

Table A 18. Sensitivity analysis for the MMVS responder rate by treatment and side of the face at Month 6, Blinded Evaluator (FAS)

As Table A 16 (only Left and Right Side Combined)

Note: Missing MMVS values are handled using multiple imputation methods.

Note: Responder is defined as a subject with an improvement of at least one grade on the MMVS from baseline.

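### The full analysis set requires injection in the Perlane-Lido arm but only randomisation in the control arm, so the primary comparison carries a one-sided post-randomisation exclusion

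*SAP*

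**What the plan says.** The FAS definition is the same in SAP section 2 and protocol 10.2: "Includes all subjects in Group B who were treated with Perlane-Lido or randomized to no-treatment group. Subjects are analyzed according to the randomisation assignment". Both name the FAS as the primary population for all efficacy analyses. In SAP Appendix A, Table A 16, the responder rate is the number of responders "divided by the number of subjects in the FAS population for the specific treatment group".

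Missing MMVS ratings up to Month 6 are filled by baseline observation carried forward (BOCF) within the FAS. SAP 3.3.2 justifies this: "This strategy is a conservative approach as it treats subjects with missing data as non-responders". The per-protocol (PP) set is a subset of the FAS.

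Protocol 4.4.2 states: "Only the evaluator will be blinded, both treating investigator and subjects will be open-labelled". On timing, protocol 4.4.1 says "Each subject will be assigned a subject number as they arrive for the treatment visit", and Table 1 of the protocol puts randomisation and first injection in the same Day 1 column. Protocol 5.5 rules out replacing withdrawn subjects and says that data collected before withdrawal will be used.

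The primary endpoint is rated "at 6 months after last treatment for the Treatment group, and at 6 months after randomization for the Control group" (SAP 1.4.1), and "baseline will be defined as the observation that is closest to but prior to study treatment on Day 1" (SAP 1.3).

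**The concern.** Entry to the primary set depends on a post-randomisation event in one arm only. A Perlane-Lido subject who is never injected leaves both numerator and denominator. A control who withdraws on Day 1 stays in the denominator as a failure. Analysing subjects as randomised does not cure this: that clause sets the arm of those already in the set, not who enters it. Subjects who are injected and withdraw later are unaffected.

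The rating is blinded, but the decision to inject is taken by people who know the allocation. The rule that the SAP calls conservative does not reach the excluded subjects, because it works only inside the FAS. The primary comparison is therefore not on all randomised subjects, and the departure can favour Perlane-Lido.

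**Working it through.** **Who is counted**

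| Subject | In FAS? | Counted as |
|---|---|---|
| Perlane-Lido, injected, withdraws before Month 6 | Yes | Non-responder (BOCF) |
| Perlane-Lido, never injected | No | Not counted |
| Control, withdraws on Day 1 | Yes | Non-responder (BOCF) |

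No visible analysis brings back the middle row. Tables A 16, A 18 (multiple imputation) and A 19 (baseline-corrected) are FAS tables, and Table A 17 uses the PP set.

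**Inputs**

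- Group B has 148 subjects at 3:1 (protocol synopsis). Check: 148 × 3/4 = 111 and 148/4 = 37, as stated. The sample-size rationale is blacked out, so 148 itself cannot be rebuilt.
- Fisher's exact test for the difference (Table A 16 notes); two-sided 5% is assumed here.
- Earlier US study, Month 2 (protocol 2.4.2): 88.7% (133/150) treated; for controls, "In the no treatment group at Month 2, the proportion of MMVS responders from baseline was 16.0% (8/50 subjects"). The present endpoint is Month 6.
- Assumed: k (randomised to Perlane-Lido, not injected), treated response of 60% or 70%, and control counts of 6/37 (about 16%) or 11/37 (about 30%).

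**Inflation of the Perlane-Lido rate**

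Let R be the responders among the 111 − k treated, and p = R/(111 − k) the FAS rate. If untreated subjects respond at rate u, the all-randomised rate is [p(111 − k) + uk]/111. The inflation is therefore (p − u) × k/111. Setting u = 0 gives the upper bound; u = 0.16 uses the earlier study's untreated rate. Example: p = 0.70, k = 3, u = 0 gives 0.70 × 3/111 = 1.89 points.

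| k | p = 70%, u = 0 | p = 70%, u = 16% | p = 88.7%, u = 0 | p = 88.7%, u = 16% |
|---|---|---|---|---|
| 1 | 0.63 | 0.49 | 0.80 | 0.65 |
| 3 | 1.89 | 1.46 | 2.40 | 1.96 |
| 6 | 3.78 | 2.92 | 4.79 | 3.93 |
| 9 | 5.68 | 4.38 | 7.19 | 5.89 |

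Entries are percentage points. With the control denominator fixed at 37, the difference between arms moves by the same amount.

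**Significance, with untreated subjects counted as failures and k = 9**

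| Treated rate | Perlane-Lido | Control | Two-sided Fisher p |
|---|---|---|---|
| about 70% (71/102) | 71/111 | 6/37 | 3.8 × 10⁻⁷ |
| about 60% (61/102) | 61/111 | 6/37 | 4.3 × 10⁻⁵ |
| about 60% (61/102) | 61/111 | 11/37 | 0.0084 |

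In the last and weakest case, p first exceeds 0.05 at k = 21 (54/111 against 11/37, p = 0.056). A verdict can turn on small k only near the boundary: with k = 3, 37/108 against 6/37 gives p = 0.040, and 37/111 gives p = 0.060. That needs a treated rate of about 34%.

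**False wins when there is no effect**

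Both arms have true rate r, and the excluded subjects are all failures, so the treated subjects respond at r × 111/(111 − k). The probability that Fisher's p ≤ 0.05 with Perlane-Lido higher (nominal 0.025), by exact enumeration:

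| r | k = 0 | k = 3 | k = 6 | k = 9 |
|---|---|---|---|---|
| 30% | 0.0195 | 0.0246 | 0.0285 | 0.0380 |
| 16% | 0.0163 | 0.0163 | 0.0212 | 0.0232 |

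If exclusion is unrelated to outcome, the 30% row becomes 0.020, 0.019, 0.017, 0.019, so there is no inflation.

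**The case against.** The strongest reply is that k is probably zero or close to it. Subjects enrol because they want midface augmentation, they are numbered on arrival for the treatment visit, and randomisation and injection are both Day 1 procedures. Disappointment with the allocation is more plausible among controls, who wait six months, and they are kept as non-responders. Nothing in the documents points to selective non-injection. This stands as an argument about size. It does not make the rule symmetric, and the rule has to be fixed before k is known.

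The larger figures also stack assumptions: k = 9 is 8% of 111, and false wins exceed 0.025 only at the assumed 30% rate, from k = 6, when exclusion removes only failures. That is accepted, and the figures are given as bounds.

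Tables A 1, A 2, A 5 and A 16 would let a reader count the excluded subjects and approximate the corrected rate. That is disclosure, not a planned analysis.

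Parts of SAP 3.3.3, SAP section 5 and the table list are blacked out and could hold an all-randomised analysis. This cannot be excluded, so the point is limited to what is visible. The FAS definition itself is complete.

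**Conclusion.** The concern holds and should be fixed. The wording of both documents creates a one-arm exclusion after randomisation, in the primary set, under open allocation. Its size depends on k, which the documents do not give. At k = 0 there is no effect, and at k = 1 the inflation is under 1 point. At k = 9 it is 4.4 to 7.2 points across the response rates assumed above. The likely damage is to the estimated rate, the difference and its confidence interval. The significance verdict is safe unless the effect is far smaller than in the earlier study or k is very large.

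**What to change.** In SAP section 2 and protocol 10.2, define the FAS as all randomised Group B subjects, analysed as randomised, with the same BOCF rule in both arms. For Perlane-Lido subjects who are never treated, add:

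1. Baseline is the last MMVS on or before Day 1, with the existing fallback to screening (SAP 1.3).
2. Month 6 is timed from randomisation, as for controls (SAP 1.4.1). The current anchor, last treatment, does not exist for them.
3. An observed Month 6 rating is used if there is one; otherwise BOCF applies.

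Add being randomised to Perlane-Lido but not treated to SAP Table 3-1, so that the PP set does not change. Keep the treated-only set as a supportive analysis, and leave the Safety population as it is.

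The cost is short edits to SAP 1.3, 1.4.1, 2 and Table 3-1, and to protocol 10.2. Protocol 12.3 requires a written amendment and ethics committee approval for a non-administrative protocol change; SAP section 5 already serves to record departures from the protocol's analysis. The visit schedule times Month 6 from last treatment, so observed ratings may be rare in these subjects, but BOCF covers their absence. No new data are needed. The reported response rate may be slightly less favourable; if every Perlane-Lido subject is injected, the results are identical.
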